11.6.2 Major Adverse Cardiovascular Events

MACE is defined as nonfatal MI, unplanned revascularization (PCI or CABG) of the ischemic target vessel including intraprocedural stent thrombosis, re-hospitalization for a CV-related condition, nonfatal stroke, CV death, and all-cause mortality.

11.6.3 Bleeding Events

Bleeding events are classified as major or minor based on BARC classification. Minor bleeding events are those that meet the criteria for BARC Type 2, and major bleeding events are those meeting the criteria for BARC Types 3 to 5.

BARC definitions are provided in Table 9.

Table 9 Bleeding Academic Research Consortium Definitions

Type	Definition
0	No bleeding
1	Bleeding that is not actionable and does not cause the patient to seek treatment
2	Any clinically overt sign of hemorrhage that “is actionable” and requires diagnostic studies, hospitalization, or treatment by a health care professional
3	
 Overt bleeding plus hemoglobin drop of 3 to < 5 g/dL (provided hemoglobin drop is related to bleed); transfusion with overt bleeding Overt bleeding plus hemoglobin drop < 5 g/dL (provided hemoglobin drop is related to bleed); cardiac tamponade; bleeding requiring surgical intervention for control; bleeding requiring intravenous vasoactive agents Intracranial hemorrhage confirmed by autopsy, imaging, or lumbar puncture; intraocular bleed compromising vision
4	Coronary artery bypass grafting-related bleeding within 48 hours
5	
 Probable fatal bleeding Definite fatal bleeding (overt or autopsy or imaging confirmation)

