5.2 Study Endpoints

5.2.1 Co-Primary Endpoints

The co-primary endpoints of this study are:

- The number of patients with target ACT (200 to 300 seconds [sec]) achieved on MT1002 (with no switch to standard of care) prior to and during PCI and PCI success. PCI success is defined as achievement of < 30% residual diameter stenosis of all treated lesions as assessed by visual inspection or Quantitative Coronary Analysis (QCA), without an in-hospital major adverse cardiac event (death, myocardial infarction [MI], or repeat coronary revascularization of the target lesion)
- AE of interest: bleeding events major (Bleeding Academic Research Consortium [BARC] Type 3–5)

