6 INVESTIGATIONAL PLAN

6.1 Description of Overall Study Design and Plan

This is an open-label, sequential-dose escalation/de-escalation trial testing 3 dose levels of MT1002 in patients undergoing PCI due to ACS with NSTEMI. Three doses of MT1002 will be sequentially tested in cohorts of 6 patients each to achieve target ACT.

Pre-specified dose escalation/de-escalation/stopping/continuation rules for the patient cohorts are shown in Table 1 below.

Table 1 Rules for Dose Escalation/De-Escalation/Stopping/Continuation

Continue to next higher dose group if:	Stop study drug infusion temporarily in an individual patient if:	Stop dose group and de-escalate according to protocol if:	Continue the same dose in the next patient cohort (to get more data for initial dose) if:	Stop the study if:
$\leq 2/6$ pat peak ACT > 300	Any ACT > 350 or < 180	$\geq 3/6$ pat peak ACT > 300	$\leq 3/6$ pat peak ACT > 300	> 3/6 pat peak ACT > 350
≥ 3 pts. peak ACT < 200 (Cohort 2)				AND
$\leq 1/6$ pat with BARC 3 to 5	BARC 3 to 5	$\geq 2/6$ pat with BARC 3 to 5	$\leq 1/6$ pat with BARC 3 to 5	> 2/6 pat with BARC 3 to 5
				OR
No SAE due to study drug	Any AE/SAE due to study drug that requires switching patient to standard of care	$\geq 2/6$ SAEs due to study drug	No SAE due to study drug	$\geq 2/6$ SAEs due to study drug

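### Table 9 prints the second Type 3 hemoglobin criterion as a drop below 5 g/dL, so read literally it counts small-drop bleeds as major in a co-primary endpoint and in the dose rules

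*Combined protocol and SAP*

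**What the plan says.** Section 11.6.3 classifies bleeding by BARC type, refers to Table 9 for the definitions, treats Type 2 as minor, and states that "major bleeding events are those meeting the criteria for BARC Types 3 to 5".

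Under Type 3, Table 9 lists three items. The first is "Overt bleeding plus hemoglobin drop of 3 to < 5 g/dL (provided hemoglobin drop is related to bleed); transfusion with overt bleeding". The second begins "Overt bleeding plus hemoglobin drop < 5 g/dL (provided hemoglobin drop is related to bleed); cardiac tamponade" and continues with "bleeding requiring surgical intervention for control; bleeding requiring intravenous vasoactive agents". The third covers intracranial and intraocular bleeding. Nothing else in Table 9 refers to hemoglobin, and no other section gives a competing hemoglobin criterion.

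The category is used in these places:
- Section 5.2.1 makes it a co-primary endpoint: "AE of interest: bleeding events major (Bleeding Academic Research Consortium [BARC] Type 3–5".
- Section 5.2.2 makes BARC Type 2 a secondary endpoint.
- Section 6.1, Table 1 (repeated in the Synopsis) uses BARC 3 to 5 in all five columns. Escalation and same-dose continuation allow at most 1/6 patients. De-escalation applies at 2/6 or more. Any such bleed is a criterion for a temporary infusion stop in that patient. One limb of the study stop requires "> 2/6 pat with BARC 3 to 5", joined by AND to more than 3/6 patients with peak ACT above 350 seconds.

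**The concern.** The second Type 3 item looks like the next grade above the first, since it adds tamponade, surgical control and vasoactive support. Its hemoglobin limit nevertheless has no floor and stops where the first band stops. A scale that takes in a 1 g/dL drop and leaves out a 6 g/dL drop is not coherent, and on the table's own logic the inequality appears reversed.

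Table 9 is the operative definition for a co-primary safety endpoint and for cohort decisions based on six patients. Sites that apply it literally would move minor bleeds into the major category and take them out of the Type 2 secondary endpoint. Sites that apply the published BARC scale from knowledge would not. With about 13 planned sites (Synopsis), the same bleed could be graded differently from one site to another.

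**Working it through.** **Step 1. Which drops meet which band.** The inputs are the two Type 3 hemoglobin criteria in Table 9, for an overt bleed with a related drop. The last column shows the reading that would make the bands adjacent.

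| Drop (g/dL) | First item, as printed | Second item, as printed | Second item, if 5 or more |
|---|---|---|---|
| 0.5, 1, 2, 2.9 | no | yes | no |
| 3, 4, 4.9 | yes | yes | no |
| 5, 6, 8 | no | no | yes |

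As printed, every drop in the first band also meets the second, so the floor of 3 g/dL does no work. With a limit of 5 or more in the second item, each drop meets at most one band and none above 3 is left out.

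**Step 2. Effect on the pooled BARC 3–5 count.**
- Drops of 3 to under 5: no effect, because both items are Type 3.
- Related drops above 0 and under 3: over-counted if they would otherwise be Type 1 or 2.
- Drops of 5 or more: under-counted only if the bleed also involves no transfusion, tamponade, surgical control, vasoactive agent, or intracranial or sight-threatening intraocular site, and is neither CABG-related within 48 hours (Type 4) nor fatal (Type 5).

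Over-counting is therefore the larger risk.

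**Step 3. Sensitivity of a six-patient cohort.** The BARC thresholds for escalation (at most 1/6) and de-escalation (at least 2/6) are complementary. A cohort with no true major bleed crosses from one to the other when two patients are reclassified.

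The documents give no expected bleeding rate, so p below is an assumed total per-patient rate of bleeds counted as BARC 3–5, with patients taken as independent:

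P(at least 2 of 6) = 1 − (1 − p)^6 − 6p(1 − p)^5

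- p = 0.05: 1 − 0.735 − 0.232 = 0.033
- p = 0.20: 1 − 0.262 − 0.393 = 0.345
- p = 0.30: 1 − 0.118 − 0.303 = 0.580 (from unrounded terms)
- p = 0.40: 1 − 0.047 − 0.187 = 0.767 (from unrounded terms)

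The plan states no figure of its own to reproduce here.

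**The case against.** Several points on the other side have force.

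- **The symbol may have been misread.** Table 9 was extracted from a PDF and one wrong character would explain everything. This cannot be excluded. However, greater-than-or-equal signs survive in many other places, including Table 1, and the original page settles the question.
- **Sites may ignore the printed wording.** Section 11.6.3 names the BARC scale, and investigators may apply it directly. Under Sections 6.1 and 14.8 the Study Management Group, which includes an independent cardiologist, weighs the criteria alongside a data review. This makes literal misgrading less likely. It does not make the definition right, and mixed practice is itself a problem for a co-primary endpoint.
- **The later SAP may redefine variables.** Section 14 lets the SAP supersede the protocol. That could repair the final tables, but not grades already used for cohort decisions.

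Three stronger readings are tempting, and the documents do not support them.

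- **That the error could stop the study.** The BARC limb also needs more than 3/6 patients with peak ACT above 350, so misgraded bleeds alone cannot trigger it.
- **That severe bleeds would generally be missed.** The routes in Step 2 remain open. A large drug-related bleed could also qualify as a serious adverse event under Section 11.6.5, and one such event already fails the no-SAE condition for escalation and for same-dose continuation.
- **That the Cohort 1 review was wrong.** The Version 6.0 entry in the summary of changes reports no major bleeding in the six patients, so there is no over-graded bleed to reverse.

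**Conclusion.** Table 9 is wrong as written, and the error sits in a decision threshold, not in background text. Its main consequence is possible over-counting of BARC 3–5 in a co-primary endpoint and in four of the five columns of Table 1: escalation, same-dose, de-escalation and individual infusion stop.

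The actual size cannot be computed from the documents. The probabilities of 3%, 34%, 58% and 77% show only how steeply the 2/6 threshold responds to the counted rate. They assume that rate, independence between patients and, for any shift between them, literal use of the table. They are not forecasts. The 20% to 40% figures are totals, not additions to a 5% base.

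Zero major bleeds in six has probability 0.262, 0.118 and 0.047 at total rates of 20%, 30% and 40%. The Cohort 1 result therefore does not exclude these rates, but it gives them no support. The correction should be made before further cohort decisions, because the threshold is easily crossed and the change is small.

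**What to change.** 1. Check the original page of Table 9 and the source BARC definition. If the symbol stands as extracted, correct the second Type 3 item so that the two hemoglobin bands are adjacent and do not overlap. On the table's own logic this is a drop of 5 g/dL or more.
2. Check that the eCRF and site instructions, which are not among the documents, use the same definition, and that the SAP does too.
3. Before the next Study Management Group decision, confirm which definition was applied to bleeds already recorded. For Cohort 1 this is a confirmation, since no major bleeds were reported.

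The cost is one symbol in the protocol, a note to sites, a check of the eCRF, and a review of the few bleeds on record. No dose or threshold in Table 1 needs to change for this point.

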11.6.4 Adverse Events of Special Interest

The AEs of interest include major bleeding events (BARC Type 3 to 5; see also Section 11.6.3), infusion reactions, hypersensitivity reactions, thrombotic events (including stent thrombosis), frequency of abrupt vessel closure, transient ischemic attack, redo of stent procedure (revascularization), or emergency CABG.

11.6.5 Serious Adverse Events

An SAE is any untoward medical occurrence, in the view of either the Investigator or Sponsor, that:

- results in death,
- is life-threatening,
- results in inpatient hospitalization or prolongation of existing hospitalization,
- results in persistent or significant disability/incapacity, and/or
- is a congenital anomaly/birth defect

Other important medical events that may not be immediately life-threatening or result in death or hospitalization, based upon appropriate medical judgment, are considered SAEs if they are thought to jeopardize the patient and/or require medical or surgical intervention to prevent one of the outcomes defining an SAE. SAEs are critically important for the identification of significant safety problems; therefore, it is important to take into account both the Investigator's and the Sponsor's assessment. If either the Sponsor or the Investigator believes that an event is serious, the event must be considered serious and evaluated by the Sponsor for expedited reporting.

11.6.6 Serious Adverse Event Reporting

An SAE occurring from the time informed consent is obtained, during the study, or within 30 days of stopping the treatment must be reported to the Zhejiang Taimei Medical Technology Co., Ltd. (Taimei) Safety and Pharmacovigilance group and will be communicated to the Sponsor. Any such SAE due to any cause, whether or not related to the study drug, must be reported within 24 hours of occurrence or when the Investigator becomes aware of the event. Notification can be made using the dedicated fax line or email for the Taimei pharmacovigilance group:

Taimei Safety and Pharmacovigilance fax numbers:

- [name] (primary)
- [name] (alternative)

Taimei Safety and Pharmacovigilance email address: [contact]

If the Investigator contacts the Taimei pharmacovigilance group by telephone, then a written report must follow within 24 hours and is to include a full description of the event and sequelae in the format detailed in the SAE reporting form.

The event must also be recorded on the standard AE eCRF. Preliminary reports of SAEs must be followed up by detailed descriptions later on, including clear and anonymized photocopies of hospital case reports, consultant reports, autopsy reports, and other documents when requested and applicable. SAE reports must be made whether or not the Investigator considers the event to be related to the investigational drug.

Appropriate remedial measures should be taken to treat the SAE, and the response should be recorded. Clinical, laboratory, and diagnostic measures should be employed as needed in order to determine the etiology of the problem. The Investigator must report all additional follow-up evaluations to the Taimei Safety and Pharmacovigilance group within 24 hours of becoming aware of the additional information or as soon as is practicable. All SAEs will be followed up until the Investigator and Sponsor agree the event is satisfactorily resolved.

Any SAE that is not resolved by the end of the study or upon discontinuation of the patient's participation in the study is to be followed up until it either resolves, stabilizes, returns to baseline values (if a baseline value is available), or is shown to not be attributable to the study drug or procedures.

11.6.7 Suspected Unexpected Serious Adverse Reactions

AEs that meet all of the following criteria will be classified as suspected unexpected serious adverse reactions (SUSARs) and reported to the appropriate regulatory authorities in accordance with applicable regulatory requirements for expedited reporting:

- serious
- unexpected (i.e., the event is not consistent with the safety information in the Investigator's Brochure)
- there is at least a reasonable possibility that there is a causal relationship between the event and the study treatment

The Investigator will assess whether an event is causally related to study treatment. The Sponsor (or Taimei Medical Technology) will consider the Investigator's assessment and determine whether the event meets the criteria for being reportable as a 7-day or 15-day safety report. SUSARs that are fatal or life-threatening must be reported to the regulatory authorities and the independent ethics committee (IEC)/institutional review boards (IRBs) (where required) within 7 days after the Sponsor (or Taimei Medical Technology) has first knowledge of them, with a follow-up report submitted within a further 8 calendar days. Other SUSARs must be reported to the relevant regulatory authorities and the IEC/IRBs within 15 calendar days after the Sponsor (or Taimei Medical Technology) first has knowledge of them.

The Sponsor (or Taimei Medical Technology) is responsible for reporting SUSARs and any other events required to be reported in an expedited manner to the regulatory authorities and for informing Investigators of reportable events, in compliance with applicable regulatory requirements within specific timeframes. Investigators will notify the relevant IEC/IRBs of reportable events within the applicable timeframes.

11.6.8 Pregnancy

Women of childbearing potential (WOCBP) must have a negative pregnancy test at Screening. An additional pregnancy test will be performed on Day 30, at the End of Study Visit.

After administration of study drug, any known cases of pregnancy in female patients or female partners of male patients will be reported up until 90 days after the date of MT1002 administration. Patients will be instructed to inform the investigator of any such pregnancies occurring during the study or for up to 90 days after MT1002 administration. The pregnancy will be reported immediately by the investigator by faxing/emailing a completed pregnancy report to the Sponsor (or designee) within 24 hours of knowledge of the event. The pregnancy will not be processed as an SAE; however, the Investigator will follow up with the patient until completion of the pregnancy and must assess the outcome in the shortest possible time but not more than 30 days after completion of the pregnancy. The Investigator should notify the Sponsor (or designee) of the pregnancy outcome by submitting a follow-up pregnancy report. If the outcome of the pregnancy involved spontaneous or therapeutic abortion (any congenital anomaly detected

in an aborted fetus is to be documented), stillbirth, neonatal death, or congenital anomaly, the Investigator will report the event by faxing/emailing a completed pregnancy report form to the Sponsor (or designee) within 24 hours of knowledge of the event.

If the Investigator becomes aware of a pregnancy occurring in the partner of a patient participating in the study, the pregnancy should be reported to the Sponsor (or designee) within 24 hours of knowledge of the event. Information regarding the pregnancy must only be submitted after obtaining written consent from the pregnant partner. The Investigator will arrange counseling for the pregnant partner by a specialist to discuss the risks of continuing with the pregnancy and the possible effects on the fetus.

Upon discontinuation from the study, only those procedures that would not expose the patient to undue risk will be performed. The Investigator should also be notified of pregnancy occurring during the study but confirmed after completion of the study. In the event that a patient is subsequently found to be pregnant after inclusion in the study, any pregnancy will be followed to term, and the status of mother and child will be reported to the Sponsor after delivery.

11.6.9 **Overdose**

The Investigator must immediately notify the Sponsor of any occurrence of overdose with study drug.

Overdose after administration of MT1002 may lead to hemorrhagic complications due to its pharmacodynamic properties. In cases of suspected overdose, it may be advisable to assess the anticoagulation status to assist in determining an excess of anticoagulant activity with a higher risk of bleeding.

12 PHARMACOKINETICS

12.1 Pharmacokinetic Sampling

12.1.1 Blood Samples

Blood samples for PK analysis of MT1002 levels will be collected at the time points indicated in the Schedule of Assessments (Table 4) and Table 5. The actual date and time of each blood sample collection will be recorded. The timing of PK samples may be altered, and/or PK samples may be obtained at additional time points to ensure thorough PK monitoring.

Details of PK blood sample collection, processing, storage, and shipping procedures are provided in a separate laboratory manual.

12.2 Pharmacokinetic Analytical Methodology

The concentration of study drug will be determined from the plasma samples using a validated analytical method. Details of the method validation and sample analysis will be included with the final clinical study report.

13 OTHER ASSESSMENTS

13.1 Biomarkers

Blood samples for analysis of PA will be collected at the visits indicated in the Schedule of Assessments (Table 4). The actual date and time of each collection will be recorded. The timing of the samples may be altered, and/or samples may be obtained at additional time points to ensure thorough monitoring.

13.2 Thrombolysis in Myocardial Infarction Flow

The TIMI flow is a scoring system assessing levels of coronary blood flow during PCI. The score ranges from 0 (no perfusion) to 3 (full perfusion) as shown in Table 10.

Table 10 Thrombolysis in Myocardial Infarction Flow Grading System

Grade	Description
0	Complete occlusion of the infarct-related artery
1	Some penetration of contrast material beyond the point of obstruction but without perfusion of the distal coronary bed
2	Perfusion of the entire infarct vessel into the distal bed but with delayed flow compared with a normal artery
3	Full perfusion of the infarct vessel with normal flow

Source: See Reference 2.

13.3 CRUSADE Bleeding Risk Score

The CRUSADE bleeding risk score ranges from 1 to 100 points with higher score indicating higher risk of bleeding: very low risk = ≤ 20 , low risk = 21 to 30, moderate risk = 31 to 40, high risk = 41 to 50, very high risk = > 50 . Patients with a CRUSADE score > 40 will be excluded from the study. Scoring will be based on the following variables: baseline hematocrit, creatinine clearance, heart rate, gender, signs of congestive heart failure, prior vascular disease, diabetes mellitus, and systolic blood pressure.

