7 SELECTION OF STUDY POPULATION

7.1 Inclusion Criteria

Individuals must meet all of the following criteria to be included in the study:

1. Males and females ≥ 18 to 85 years of age.
2. Diagnosed with NSTEMI defined as new or presumably new ST-segment depression of at least 1 mm in 2 contiguous leads, T-wave inversion more than 3 mm, or any dynamic ST shifts, or elevated troponin I (or troponin T if the local site does not have the troponin I test) higher than upper limit of normal (ULN), or CK-MB consistent with the universal definition of MI.
3. Patients who will undergo PCI during the index hospitalization for an NSTEMI (ideally patients start of PCI within 96 hours of presenting to the emergency room/ hospital).
4. Ability to understand and willing to give written informed consent. Signed informed consent form before any study related activities.
5. Women of childbearing potential (WOCBP) must have a negative pregnancy test or be post-menopausal for at least 1 year before enrollment or be permanently sterilized since ≥ 6 weeks (i.e., documented hysterectomy, bilateral salpingectomy, or bilateral oophorectomy). Females of childbearing potential and males with partners of childbearing potential must be using effective contraception if they become sexually active from the time of consent to 90 days after the MT1002 infusion day (i.e., any double combination of male or female condom with spermicidal gel, diaphragm, sponge, or cervical cap with spermicidal gel). Women who are breastfeeding are excluded. For the definition and list of allowed highly effective methods of contraception, see APPENDIX 1.

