7.2 Exclusion Criteria

Individuals meeting any of the following criteria at Screening are ineligible to participate in this study:

1. Cardiogenic shock or prolonged cardiopulmonary resuscitation (CPR).
2. Active bleeding, bleeding diathesis, coagulopathy.
3. Any history of intracranial bleeding or structural abnormalities (intracerebral mass, aneurysm, arteriovenous malformation [AVM]).
4. Prior transient ischemic attack, prior stroke within 6 months.
5. Index MI is STEMI (ST elevation Myocardial Infraction).
6. The following planned procedures within 30 days after enrollment: CABG, valve surgery, or additional invasive procedures.
7. Requirement for oral anticoagulants before Day 7 post IP treatment.
8. Based on investigator's discretion, subject is at high bleeding risk, i.e., CRUSADE (Can Rapid risk stratification of Unstable angina patients Suppress ADverse outcomes with Early implementation of the American College of Cardiology/American Heart Association [ACC/AHA] Guidelines) bleeding risk score >60.
9. Suspected aortic dissection.
10. History of gastrointestinal or genitourinary bleeding within the previous 3 months.
11. Refusal to receive blood transfusion if needed during the study.
12. Major surgery in the last month.
13. History of heparin-induced thrombocytopenia and bleeding diathesis.
14. Severe uncontrolled hypertension, defined as a systolic blood pressure > 180 mmHg and diastolic blood pressure > 100 mmHg up to 24 hours of adequate treatment.
15. Prior (within 30 days prior to enrollment) or planned administration of thrombolytics, glycoprotein IIb/IIIa inhibitors, bivalirudin, or fondaparinux for the index MI. Subcutaneous injections of unfractionated heparin and low molecular weight heparin are allowed up to 4 hours and 8 hours, respectively, before study drug. Use of intravenous unfractionated heparin may be continued up until the time of enrollment (just prior to PCI), if ACT is < 200 seconds.
16. Known relevant hematological deviations: hemoglobin (male) < 11 g/dL hemoglobin (female) < 10 g/dL, hematocrit < 35%, platelet count < 100,000 cells/ μ L.
17. Use of Coumadin derivatives and/or Factor Xa inhibitor drugs within the last 7 days.

18. Chronic therapy with non-steroidal anti-inflammatory drugs (NSAIDs; except aspirin) (NSAID use is defined as chronic if these medications are taken more than three times a week for more than three months), cyclooxygenase (COX)-2 inhibitors within 1 month before screening.

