Clopidogrel: On admission, all patients will receive a loading dose of clopidogrel (600 mg) if not already on a maintenance dose, and then stay on a maintenance dose of 75 mg/day. Patients should continue this ADP/P2Y₁₂ inhibitor for the remainder of the study period (i.e., through 30 days post-dose) or longer per local standard of care, as outlined by the current ACCF/AHA and European Society of Cardiology Guidelines.

Ticagrelor or Prasugrel: if the local clinical guidance recommends use of Ticagrelor or Prasugrel, the recommended doses will be: On admission, all patients will receive a loading dose of Ticagrelor 180 mg if not already on a maintenance dose, and then stay on a maintenance dose of 90 mg twice daily. Or on admission, all patients will receive a loading dose of Prasugrel 60 mg if not already on a maintenance dose, and then stay on a maintenance dose of 5-10 mg daily. Patients should continue this ADP/P2Y₁₂ inhibitor for the remainder of the study period (i.e., through 30 days post-dose) or longer per local standard of care, as outlined by the current ACCF/AHA and European Society of Cardiology Guidelines.

In this study, clopidogrel (or Ticagrelor or Prasugrel) and acetylsalicylic acid are considered non-investigational medicinal products. This means that in the event of an SAE, the Investigator will assess the causal relationship of the SAE to the non-investigational medicinal product.

Bivalirudin: Patients receiving bivalirudin before enrollment into the study for the index MI should not be included in the study. Patients who fail to achieve the ACT target of 200 to 300 sec with MT1002 (within 30 minutes after MT1002 infusion initiation) can be switched to bivalirudin before PCI as a standard of care. Bivalirudin cannot be administered simultaneously with MT1002; MT1002 treatment should be discontinued at least 30 mins before switching to bivalirudin (dosing per local standard of care).

Glycoprotein IIb/IIIa inhibitors: Upstream use of glycoprotein IIb/IIIa inhibitors (i.e., within 24 hours before enrollment) is an exclusion criterion. After enrollment, glycoprotein IIb/IIIa inhibitors may be used as bail out for procedural or angiographic complications or clinical instability (dosing per local standard of care). Glycoprotein IIb/IIIa inhibitors cannot be administered simultaneously with MT1002; MT1002 treatment should be discontinued 30 minutes before switching to glycoprotein IIb/IIIa inhibitors.

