9 STUDY PROCEDURES

Table 4 outlines the timing of procedures and assessments to be performed throughout the study. Section 11.5 specifies laboratory assessment samples to be obtained. See Sections 100 and 111 for additional details regarding efficacy/pharmacodynamic assessments and safety assessments, respectively.

Table 4 Schedule of Assessments

Assessment	Screening	Day of Procedure, Day 1			Follow-up		
Study Day	On admission	Pre PCI (Baseline)	During PCI ^a (≤ 72 hours from admission depending on the risk criteria)	Post PCI	Day 2 ^b	Day 14±1	End of Study Day 30±2
Informed consent	X						
Inclusion/exclusion criteria	X	X					
Significant medical and surgical history	X						
Demographics	X						
Cardiac and noncardiac medication on	X						
Physical examination ^c	X			X	X	X	X
Weight, height, body mass index	X						
Vital signs		X ^l	X	X	X	X	X
12-lead electrocardiogram		X ^l		X	X	X	X
CK-MB, cardiac troponin I (or troponin T) ^d		X ^l X	X	X	X	X	X
ACT, aPTT, PT, TT, FIB, INR		X ^l	X ^k	X	X	X	X
PA (by PFA100 or PFA200) ^e		X ^l	X	X	X	X	X
Hematocrit, hemoglobin, platelet count, RBC and WBC counts		X ^l	X	X	X	X	X
Serum chemistry including lipid panel and HbA1c ^f	X				X	X	X
Serum or urine pregnancy test (women of childbearing potential only)	X						X
Percutaneous coronary intervention			X				
Aspirin ^g	X	(X)			◀-----▶		
Clopidogrel (or Ticagrelor or Prasugrel) ^h	X	(X)			◀-----▶		
Enrollment to MT1002		X					
Administration of MT1002 ⁱ		X	X	X			
TIMI flow grade		X	X				
Pharmacokinetic blood sampling ^j		X	X	X	X		
Concomitant medication review	X	X	X	X	X	X	X
Bleeding adverse events (BARC)		X	X	X	X	X	X
Other adverse events	X						

Assessment	Screening	Day of Procedure, Day 1			Follow-up		
Study Day	On admission	Pre PCI (Baseline)	During PCI ^a (≤ 72 hours from admission depending on the risk criteria)	Post PCI	Day 2 ^b	Day 14±1	End of Study Day 30±2
Discharge					X		
Study close out							X

Abbreviations: ACT, activated clotting time; aPTT, activated partial thromboplastin time; BARC, Bleeding

Academic Research Consortium; CK, creatine kinase; HbA1c, glycosylated hemoglobin; min, minutes; PA, platelet aggregation; PCI, percutaneous coronary intervention; PT, prothrombin time; RBC, red blood cell; sec, seconds; TIMI, thrombolysis in myocardial infarction; WBC, white blood cell.

- ^a PCI should start after MT1002 initiation as soon as ACT is confirmed to be ≥ 200 sec or within 30 min after MT1002 start, whichever occurs first.

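### Section 13.3 excludes CRUSADE scores above 40 while exclusion criterion 8 uses above 60, so sites can apply different bleeding-risk cut-offs in a trial whose dose decisions count major bleeds

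*Combined protocol and SAP*

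**What the plan says.** **CRUSADE.** Section 13.3 is unqualified: "Patients with a CRUSADE score > 40 will be excluded from the study". It also sets out the risk bands, ending with "high risk = 41 to 50, very high risk = > 50". Exclusion criterion 8 (Section 7.2, same threshold in the synopsis) excludes patients whom the investigator judges to be at high bleeding risk, equated with a "bleeding risk score >60". Section 9.2.1 has sites obtain the score at screening and then check eligibility against the inclusion and exclusion criteria.

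**Where bleeding enters the decisions.** BARC 3–5 bleeding is a co-primary endpoint (Section 5.2.1). Table 1 in Section 6.1 allows at most 1 of 6 patients with such a bleed for escalating or for continuing the same dose, and lists 2 or more of 6 as a criterion for de-escalation.

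**Two further wording differences.** Criterion 15 excludes "Prior (within 30 days prior to enrollment) or planned administration of thrombolytics, glycoprotein IIb/IIIa inhibitors, bivalirudin, or fondaparinux for the index MI". Section 8.5.1 restates part of this as "Upstream use of glycoprotein IIb/IIIa inhibitors (i.e., within 24 hours before enrollment) is an exclusion criterion". Inclusion criterion 3 asks for PCI during the index hospitalisation, ideally "within 96 hours of presenting to the emergency room/ hospital"; the Table 4 column heading gives at most "72 hours from admission depending on the risk criteria".

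**The concern.** The two CRUSADE passages give different answers for every score from 41 to 60. On the protocol's own scale that interval is the whole of the high band (41–50) and part of the very high band (above 50). It therefore concerns patients whom the protocol itself places at raised bleeding risk.

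A site that enrols a patient scoring 55 satisfies the number in criterion 8 and breaches Section 13.3. Whether that must be reported as a deviation under Section 15.7.2 cannot be settled from the text. A stricter site would turn the same patient away.

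The statistical consequence comes from the design. Cohorts are small, enrolled one after another, and not randomised. If the share of patients scoring 41–60 differs between cohorts, nothing in the design separates that difference from the effect of dose, and bleed counts are among the inputs to the dose decision.

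**Working it through.** **1. The plan's own figure.** Sections 1 and 14.1 give up to 18 enrolled, 40% screen failure and about 30 screened: 18 / (1 − 0.40) = 30. This reproduces and is not in dispute. The 18 itself rests on clinical experience, and no bleeding rate is given anywhere in the plan.

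**2. The CRUSADE passages side by side.**

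| Score | Section 13.3 | Criterion 8 (7.2, synopsis) |
|---|---|---|
| up to 40 | not excluded | not excluded by score |
| 41–50 (high) | excluded | not excluded by score |
| 51–60 (part of very high) | excluded | not excluded by score |
| above 60 | excluded | excluded |

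The middle two rows are the conflict. Under criterion 8 the investigator may still exclude such a patient by judgement, which leaves room for further variation between sites.

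**3. What case mix could do to a six-patient cohort (illustration, assumed rates).** Let b be the bleed risk in ordinary patients, h the risk in higher-risk patients, and k the number of higher-risk patients among six. Patients are taken as independent.

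- P(0) = (1−h)^k × (1−b)^(6−k)
- P(1) = k·h·(1−h)^(k−1)·(1−b)^(6−k) + (6−k)·b·(1−b)^(5−k)·(1−h)^k
- P(2 or more of 6) = 1 − P(0) − P(1)

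With b = 5% and h = 15%:

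- k = 0: 1 − 0.73509 − 0.23213 = 0.033
- k = 3: 1 − 0.52654 − 0.36189 = 0.112
- k = 6: 1 − 0.37715 − 0.39933 = 0.224

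The same formula with b = 5% and three values of h:

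| k of 6 at higher risk | h = 10% | h = 15% | h = 20% |
|---|---|---|---|
| 0 | 3.3% | 3.3% | 3.3% |
| 1 | 4.3% | 5.3% | 6.3% |
| 2 | 5.5% | 8.0% | 10.8% |
| 3 | 6.8% | 11.2% | 16.2% |
| 6 | 11.4% | 22.4% | 34.5% |

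The dose is the same throughout; only the mix of patients changes. Six is the main planned cohort size, but the third cohort is listed as 6–8, and the synopsis gives 3–6 for a de-escalated second cohort.

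**4. The other two differences.** A patient given a glycoprotein IIb/IIIa inhibitor for the index MI between 24 hours and 30 days before enrolment is caught by criterion 15 and not by the wording in 8.5.1. But 8.5.1 opens by sending the reader to Section 7.2 for the therapies that exclude a patient, so it describes that list and does not compete with it. For PCI timing, one figure is qualified as ideal and the other as depending on risk criteria, and they run from presentation and from admission respectively. The documents draw no link between PCI timing and bleeding.

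**The case against.** The strongest reply is that Section 9.2.1 points sites to the inclusion and exclusion criteria, that 7.2 and the synopsis agree on a score above 60, and that the outlier is one sentence under Other Assessments. That makes uniform practice plausible, but it does not remove the conflict: Section 13.3 is current text, says without qualification that such patients are excluded, and no passage ranks it below 7.2. The change log suggests how the mismatch may have arisen, since version 5.0 narrowed the bleeding-risk criterion. It does not tell a site which current sentence to follow, and this point does not rest on it.

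Some stronger readings are tempting and are not supported:

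- *That sites will enrol populations with different bleeding risk.* The text shows that they can. Nothing shows that any patient scoring 41–60 was enrolled.
- *That three equal contradictions drive the bleeding risk.* The CRUSADE conflict carries the argument. The glycoprotein wording is a loose paraphrase of the list to which its own section refers, and the PCI window does not support the bleeding argument at all.
- *That the chance of de-escalation rises from 3.3% to 22%.* This needs assumed rates and all six patients at triple the risk.
- *That two bleeds force de-escalation automatically.* Section 6.1 has the Study Management Group weigh safety, efficacy and drug concentration together with the Table 1 criteria, and Section 14.8 includes an independent cardiologist in the group.

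It is also fair to say that the analysis is descriptive, that Section 14 already lists all data, and that six-patient cohorts would separate dose from case mix poorly even under one cut-off. This limits what the fix can achieve, but it is no reason to leave an avoidable source of variation in an eligibility rule.

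**Conclusion.** The concern holds for CRUSADE. Scores of 41 to 60 are ineligible under Section 13.3 and not excluded by score under criterion 8. This is more than a clerical slip, because the rule governs bleeding risk in a trial that counts major bleeds both as a co-primary endpoint and in its dose rules.

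The size of any effect is unknown. With assumed risks of 5% and 15%, one to three higher-risk patients in a cohort would move the chance of meeting the two-bleed criterion from 3.3% to between 5.3% and 11.2%; 22.4% is the extreme. Higher-risk rates of 10% or 20% would give 4.3% to 6.8%, or 6.3% to 16.2%, for the same one to three patients. None of these rates comes from the documents, and no sample-size figure changes. The glycoprotein IIb/IIIa and PCI-window differences are minor alignment items.

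**What to change.** 1. Reconcile Section 13.3 with criterion 8 in Section 7.2 and the synopsis so that one CRUSADE rule applies, stating how the score and the investigator's discretion combine. The sponsor decides the value.
2. Add to the analysis plan a summary of the screening CRUSADE score by cohort, shown beside BARC 3–5 bleeding, and identify any enrolled patients who scored 41–60. Section 14 promises listings of all data but does not specify this summary.
3. In the same amendment, align the look-back in 8.5.1 with criterion 15, and the Table 4 heading with inclusion criterion 3, again with the values left to the sponsor.

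The cost is amendment wording and one descriptive table. The score is already obtained at screening, so no new data collection is needed. The reconciliation should be in place before more patients are enrolled.
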